10.1.4 Data protection

All personal data collected and/or processed in relation to this study will be handled in compliance with all applicable Privacy & Data Protection laws and regulations, including the GDPR. The study Sponsor is the Sanofi company responsible for ensuring compliance with this matter, when processing data from any individual who may be included in the Sanofi databases, including Investigators, nurses, experts, service providers, Ethics Committee members, etc.

When archiving or processing personal data pertaining to the Investigator and/or to the participants, the Sponsor takes all appropriate measures to safeguard and prevent access to this data by any unauthorized third party.

Protection of participant data

Data collected must be adequate, relevant and not excessive, in relation to the purposes for which they are collected. Each category of data must be properly justified and in line with the study objective.

Participant race and ethnicity will be collected in this study because they are required by regulatory agencies (eg, on African American population for the FDA or on Japanese population for the Pharmaceuticals and Medical Devices Agency in Japan). They will not be collected in the countries where this is prohibited by local regulation.

- Participants will be assigned a unique identifier by the Sponsor. Any participant records or datasets that are transferred to the Sponsor or its service providers will be identifiable only by the unique identifier; participant names or any information which would make the participant identifiable will not be transferred to the Sponsor.
- The participant must be informed that his/her personal study-related data will be used by the Sponsor in accordance with applicable data protection laws. The level of disclosure must also be explained to the participant as described in the informed consent.
- The participant must be informed that his/her medical records may be examined by Clinical Quality Assurance auditors or other authorized personnel appointed by the Sponsor, by appropriate IRB/IEC members, and by inspectors from regulatory authorities.
- Participants must be informed that their study-related data will be used for the whole "drug development program", ie, for this trial as well as for the following steps necessary for the development of the investigational product, including to support negotiations with payers and publication of results.

Protection of data related to professionals involved in the study

- Personal data (eg, contact details, affiliation(s) details, job title and related professional information, role in the study, professional resume, training records) are necessary to allow Sanofi to manage involvement in the study and/or the related contractual or pre-contractual relationship. They may be communicated to any company of the Sanofi group ("Sanofi") or to Sanofi service providers, where needed.
- Personal data can be processed for other studies and projects. At any time, objection to processing can be made by contacting the Sanofi Data Protection Officer (link available at Sanofi.com).
- In case of refusal to the processing of personal data by or on behalf of Sanofi, it will be impossible to involve the professionals in any Sanofi study. In case the professionals have already been involved in a Sanofi study, they will not be able to object to the processing of their personal data as long as they are required to be processed by applicable regulations. The same rule applies in case the professionals are listed on a regulatory agencies disqualification list.
- Personal data can be communicated to the following recipients:
 - Personnel within Sanofi or partners or service providers involved in the study,
 - Judicial, administrative and regulatory authorities, in order to comply with legal or regulatory requirements and/or to respond to specific requests or orders in the framework of judicial or administrative procedures. Contact details and identity may also be published on public websites in the interest of scientific research transparency.

- Personal data may be transferred towards entities located outside the Economic European Area, in countries where the legislation does not necessarily offer the same level of data protection or in countries not recognized by the European Commission as offering an adequate level of protection. Those transfers are safeguarded by Sanofi in accordance with the requirement of European law including, notably:
 - The standard contractual clauses of the European Commission for transfers towards our partners and service providers,
 - Sanofi's Binding Corporate Rules for intra-group transfers.
- Professionals have the possibility to lodge a complaint with Sanofi leading Supervisory Authority, the "Commission Nationale de l'Informatique et des Libertés" (CNIL) or with any competent local regulatory authority.
- Personal data of professionals will be retained by Sanofi for up to thirty (30) years, unless further retention is required by applicable regulations.
- In order to facilitate the maintenance of Investigators personal data, especially if they contribute to studies sponsored by several pharmaceuticals companies, Sanofi participates in the Shared Investigator Platform (SIP) and in the TransCelerate Investigator Registry (IR) project (https://transceleratebiopharmainc.com/initiatives/investigator-registry/). Therefore, personal data will be securely shared by Sanofi with other pharmaceutical company members of the TransCelerate project. This sharing allows Investigators to keep their data up-to-date once for all across pharmaceutical companies participating in the project, with the right to object to the transfer of the data to the TransCelerate project.
- Professionals have the right to request the access to and the rectification of their personal data, as well as their erasure (where applicable) by contacting the Sanofi Data Protection Officer: Sanofi DPO [name] (to contact Sanofi by email, visit https://www.sanofi.com/en/our-responsibility/sanofi-global-privacy-policy/contact).

10.1.5 Committees structure

Not applicable.

10.1.6 Dissemination of clinical study data

Study participants

Sanofi shares information about clinical trials and results on publicly accessible websites, based on company commitments, international and local legal and regulatory requirements, and other clinical trial disclosure commitments established by pharmaceutical industry associations. These websites include clinicaltrials.gov, EU clinicaltrialregister (eu.ctr), and sanofi.com, as well as some national registries.

In addition, results from clinical trials in participants are required to be submitted to peer-reviewed journals following internal company review for accuracy, fair balance and

intellectual property. For those journals that request sharing of the analyzable data sets that are reported in the publication, interested researchers are directed to submit their request to clinicalstudydatarequest.com.

Individual participant data and supporting clinical documents are available for request at clinicalstudydatarequest.com. While making information available we continue to protect the privacy of participants in our clinical trials. Details on data sharing criteria and process for requesting access can be found at this web address: clinicalstudydatarequest.com.

Professionals involved in the study or in the drug development program

Sanofi may publicly disclose, and communicate to relevant authorities/institutions, the funding, including payments and transfers of value, direct or indirect, made to healthcare organizations and professionals and/or any direct or indirect advantages and/or any related information or document if required by applicable law, by regulation or by a code of conduct such as the "The European Federation of Pharmaceutical Industries and Associations (EFPIA) Code on Disclosure of Transfers of Value from Pharmaceutical Companies to Healthcare Professionals and Healthcare Organisations".

10.1.7 Data quality assurance

- All participant data relating to the study will be recorded on printed or electronic CRF unless transmitted to the Sponsor or designee electronically (eg, laboratory data). The Investigator is responsible for verifying that data entries are accurate and correct by physically or electronically signing the CRF.
- Guidance on completion of CRFs will be provided in CRF completion instructions.
- The Investigator must permit study-related monitoring, audits, IRB/IEC review, and regulatory agency inspections and provide direct access to source data documents.
- Quality tolerance limits (QTLs) will be pre-defined to identify systematic issues that can impact participant safety and/or reliability of study results. These pre-defined parameters will be monitored during the study and important deviations from the QTLs and remedial actions taken will be summarized in the clinical study report.
- Monitoring details describing strategy, including definition of study critical data items and processes (eg, risk-based initiatives in operations and quality such as risk management and mitigation strategies and analytical risk-based monitoring), methods, responsibilities, and requirements, including handling of noncompliance issues and monitoring techniques (central, remote, or on-site monitoring) are provided in separate study documents.
- The Sponsor or designee is responsible for the data management of this study, including quality checking of the data.
- The Sponsor assumes accountability for actions delegated to other individuals (eg, contract research organizations).
- Records and documents, including signed ICFs, pertaining to the conduct of this study must be retained by the Investigator for 25 years after the signature of the final study

report unless local regulations or institutional policies require a longer retention period. No records may be destroyed during the retention period without the written approval of the Sponsor. No records may be transferred to another location or party without written notification to the Sponsor.

10.1.8 Source documents

- Source documents provide evidence for the existence of the participant and substantiate the integrity of the data collected. Source documents are filed at the Investigator's site.
- Data reported on the CRF or entered in the eCRF that are transcribed from source documents must be consistent with the source documents or the discrepancies must be explained. The Investigator may need to request previous medical records or transfer records, depending on the study. Also, current medical records must be available.
- Every data point recorded in the CRF must have a source document. The Investigator/delegated site staff will report all the original data in the participant's medical chart or in a study specific source document created by him/her. If such document is used, the template should be reviewed by the clinical research associate (CRA). A list of source document and their location will be filed in the Investigator Study File.
- The Investigator must maintain accurate documentation (source data) that supports the information entered in the CRF.
- Study monitors will perform ongoing source data verification to confirm that data entered into the CRF by authorized site personnel are accurate, complete, and verifiable from source documents; that the safety and rights of participants are being protected; and that the study is being conducted in accordance with the currently approved protocol and any other study agreements, ICH GCP, and all applicable regulatory requirements.

10.1.9 Study and site start and closure

First act of recruitment

The study start date is the date on which the clinical study will be open for recruitment of participants.

The first act of recruitment is the first site open is considered the first act of recruitment and will be the study start date.

Study/Site termination

The Sponsor or designee reserves the right to close the study site or terminate the study at any time for any reason at the sole discretion of the Sponsor. Study sites will be closed upon study completion. A study site is considered closed when all required documents and study supplies have been collected and a study-site closure visit has been performed.

The Investigator may initiate study-site closure at any time, provided there is reasonable cause and sufficient notice is given in advance of the intended termination.

Reasons for study termination by the Sponsor, as well as reasons for the early closure of a study site by the Sponsor or Investigator may include but are not limited to:

- For study termination:
 - Information on the product leads to doubt as to the benefit/risk ratio,
 - Discontinuation of further study intervention development.
- For site termination:
 - Failure of the Investigator to comply with the protocol, the requirements of the IRB/IEC or local health authorities, the Sponsor's procedures, or GCP guidelines,
 - Inadequate or no recruitment (evaluated after a reasonable amount of time) of participants by the Investigator,
 - Total number of participants included earlier than expected.

If the study is prematurely terminated or suspended, the Sponsor shall promptly inform the Investigators, the IECs/IRBs, the regulatory authorities, and any contract research organization(s) used in the study of the reason for termination or suspension, as specified by the applicable regulatory requirements. The Investigator shall promptly inform the participant and should assure appropriate participant therapy and/or follow-up.

10.1.10 Publication policy

- The results of this study may be published or presented at scientific meetings. If this is foreseen, the Investigator agrees to submit all manuscripts or abstracts to the Sponsor before submission. This allows the Sponsor to protect proprietary information and to provide comments.
- The Sponsor will comply with the requirements for publication of study results. In accordance with standard editorial and ethical practice, the Sponsor will generally support publication of multicenter studies only in their entirety and not as individual site data. In this case, a coordinating Investigator will be designated by mutual agreement.
- Authorship will be determined by mutual agreement and in line with International Committee of Medical Journal Editors authorship requirements.

10.2 APPENDIX 2: CLINICAL LABORATORY TESTS

- The tests detailed in Table 9 will be performed by the local laboratory with the exception PK/Circulating CEACAM5, ATA, cfDNA/Germline DNA, and tumor DNA/RNA analysis and some additional circulating CEA, which will be performed in the central laboratory or another external laboratory.
- Protocol-specific requirements for inclusion or exclusion of participants are detailed in Section 5 of the protocol.

- Additional tests may be performed at any time during the study as determined necessary by the Investigator or required by local regulations.
- Pregnancy testing should be conducted in all WOCBP at Screening, then every 4 weeks from Cycle 2 before each IMP administration, and at the EOT, as detailed in the SoA (Section 1.3). Women of childbearing potential must have a negative serum pregnancy test result within 7 days prior to the initial intervention and at the EOT evaluation (30 ±5 days after the last IMP administration).

Laboratory tests	Parameters	
Hematology		
	Platelet count	
	Red blood cell (RBC) count	
	Hemoglobin	
	Hematocrit	
	White blood cell (WBC) count with differential:	
	Neutrophils ^a	
	Lymphocytes	
	Monocytes	
	Eosinophils	
	Basophils	
Coagulation	International normalized ration (INR)	
Clinical chemistry ^b		
	Urea or Blood urea nitrogen (BUN)	
	Creatinine-eGFR (estimated glomerular filtration rate)	
	Glucose	
	Potassium	
	Sodium	
	Phosphate	
	Chloride	
	Calcium	
	Aspartate aminotransferase (AST)/ Serum glutamic-oxaloacetic transaminase (SGOT)	
	Alanine aminotransferase (ALT)/ Serum glutamic-pyruvic transaminase (SGPT)	
	Lactate dehydrogenase (LDH)	
	Alkaline phosphatase (ALP)	
	Total and direct bilirubin	
	Total protein	
	Albumin	
	Circulating carcinoembryonic antigen (CEA) (local assessment)	
Pregnancy testing	Serum or highly sensitive urine human chorionic gonadotropin (hCG) pregnancy	
	test (as needed for women of childbearing potential) ^c	
Other screening tests	 Serology (Human immunodeficiency virus [HIV] antibody, hepatitis B surface antigen [HBsAg] or hepatitis B viral DNA, and hepatitis C virus antibody or Hepatitis C virus [HCV], RNA), and immunoglobulin G [IgG] if applicable as per local regulatory requirement 	

Table 9 - Protocol-required laboratory tests

27-Sep-2021	
Version number: 1	

Parameters
 Additional circulating carcinoembryonic antigen (CEA) and circulating CEACAM5 (central assessment)
 Fresh biopsy as optional, for CEACAM5 expression status and DNA/RNA analysis (central assessment).
cfDNA/Germline DNA analysis on blood (central)
 PK samples and anti-therapeutic antibody (ATA) (Central)
 Follicle-stimulating hormone and estradiol (as needed in women of nonchildbearing potential only).

NOTES:

a If Grade 4 neutropenia, assess ANC every 2 to 3 days until ANC $\geq 0.5 \times 10^{9}$ /L.

b Details of liver chemistry stopping criteria and required actions and follow-up assessments after liver stopping or monitoring event are given in Section 8.2.6.6. All events of ≥ Grade 3 ALT/AST increase must be reported as an adverse event of special interest (AESI).

c Local urine testing will be standard for the protocol unless serum testing is required by local regulation or Institutional review board/Independent Ethics Committee. In addition, serum pregnancy test is mandatory for screening and end-of the treatment (EOT) evaluation

Investigators must document their review of each laboratory safety report.

10.3 APPENDIX 3: AES AND SAES: DEFINITIONS AND PROCEDURES FOR RECORDING, EVALUATING, FOLLOW-UP, AND REPORTING

10.3.1 Definition of AE

AE definition

- An AE is any untoward medical occurrence in a patient or clinical study participant, temporally associated with the use of study intervention, whether or not considered related to the study intervention.
- NOTE: An AE can therefore be any unfavorable and unintended sign (including an abnormal laboratory finding), symptom, or disease (new or exacerbated) temporally associated with the use of study intervention.

Definition of unsolicited and solicited AE

- An unsolicited adverse event is an adverse event that was not solicited using a participant diary and that is communicated by a participant who has signed the informed consent. Unsolicited AEs include serious and nonserious AEs.
- Potential unsolicited AEs may be medically attended (ie, symptoms or illnesses requiring a hospitalization, emergency room visit, or visit to/by a health care provider). The participants will be instructed to contact the site as soon as possible to report medically attended event(s), as well as any events that, though not medically attended, are of participant concern. Detailed information about reported unsolicited AEs will be collected by qualified site personnel and documented in the participant's records.

- Unsolicited AEs that are not medically attended nor perceived as a concern by the participant will be collected during an interview with the participants and by review of available medical records at the next visit.
- Solicited AEs are predefined local and systemic events for which the participant is specifically questioned, and which are noted by the participants in their diary.

Events meeting the AE definition

- Any abnormal laboratory test results (hematology, clinical chemistry, or urinalysis) or other safety assessments (eg, ECG, radiological scans, vital signs measurements), including those that worsen from baseline, considered clinically significant in the medical and scientific judgment of the Investigator (ie, not related to progression of underlying disease), eg:
 - Leading to IMP discontinuation or modification of dosing, and/or,
 - Fulfilling a seriousness criterion, and/or,
 - Defined as an AESI.
- Exacerbation of a chronic or intermittent pre-existing condition including either an increase in frequency and/or intensity of the condition.
- New condition detected or diagnosed after study intervention administration even though it may have been present before the start of the study.
- Signs, symptoms, or the clinical sequelae of a suspected drug-drug interaction.
- Signs, symptoms, or the clinical sequelae of a suspected overdose of either study intervention or a concomitant medication.
- Lack of efficacy or failure of expected pharmacological action per se will not be reported as an AE or SAE. Such instances will be captured in the efficacy assessments. However, the signs, symptoms, and/or clinical sequelae resulting from lack of efficacy will be reported as AE or SAE if they fulfill the definition of an AE or SAE.
- The signs, symptoms, and/or clinical sequelae resulting from lack of efficacy will be reported as an AE or SAE if they fulfill the definition of an AE or SAE. Also, lack of efficacy or failure of expected pharmacological action also constitutes an AE or SAE.

Events NOT meeting the AE definition

- Any clinically significant abnormal laboratory findings or other abnormal safety assessments that are associated with the underlying disease, unless judged by the Investigator to be more severe than expected for the participant's condition.
- The disease/disorder being studied or expected progression, signs, or symptoms of the disease/disorder being studied, unless more severe than expected for the participant's condition.
- Medical or surgical procedure (eg, endoscopy, appendectomy): the condition that leads to the procedure is the AE.

- Situations in which an untoward medical occurrence did not occur (social and/or convenience admission to a hospital).
- Anticipated day-to-day fluctuations of pre-existing disease(s) or condition(s) present or detected at the start of the study that do not worsen.

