8.3.7 Adverse events of special interest

An AESI is an AE (serious or nonserious) of scientific and medical concern specific to the Sponsor's product or program, for which ongoing monitoring and immediate notification by the

Investigator to the Sponsor is required. Such events may require further investigation in order to characterize and understand them. Adverse events of special interest may be added, modified or removed during a study by protocol amendment.

- Pregnancy of a female participant entered in a study as well as pregnancy occurring in a female partner of a male participant entered in a study with IMP;
 - Pregnancy occurring in a female participant entered in the clinical trial or in a female partner of a male participant entered in the clinical trial. It will be qualified as an SAE only if it fulfills one of the seriousness criteria (see Appendix 3 [Section 10.3]),
 - In the event of pregnancy in a female participant, IMP should be discontinued,
 - Follow-up of the pregnancy in a female participant or in a female partner of a male participant is mandatory until the outcome has been determined (See Appendix 4 [Section 10.4])
- Symptomatic overdose (serious or nonserious) with IMP
 - An overdose (accidental or intentional) with the IMP is an event suspected by the Investigator or spontaneously notified by the participant (not based on systematic pills count) and defined as an increase of at least 30% of the dose to be administered in the specified duration or if the dose is administered in less than half the recommended duration of administration.
- Grade \geq 3 keratopathy/keratitis.
- Bundle branch blocks or any conduction defects.
- Grade \geq 3 liver enzyme increased (symptomatic or asymptomatic).

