 - Intensive treatment in an emergency room or at home for:
 - Allergic bronchospasm,
 - Blood dyscrasias (ie, agranulocytosis, aplastic anemia, bone marrow aplasia, myelodysplasia, pancytopenia, etc),
 - Convulsions (seizures, epilepsy, epileptic fit, absence, etc).
 - Development of drug dependence or drug abuse,
 - ALT >3 × ULN + total bilirubin >2 × ULN or asymptomatic ALT increase >10 × ULN,
 - Suicide attempt or any event suggestive of suicidality,
 - Syncope, loss of consciousness (except if documented as a consequence of blood sampling),
 - Bullous cutaneous eruptions.

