- For each liver function test (eg, ALT), participants having experienced a PCSA (eg, ALT >5 ULN) will be summarized using the following categories: Returned to baseline PCSA status (or returned to value ≤ ULN in case of missing baseline) before last IMP dose, Returned to baseline PCSA status after last IMP dose, Never returned to baseline PCSA status, No assessment after elevation. This summary will be performed by categories of elevation (ALT >3, >5, >10, >20 ULN).
- A listing of possible Hy's law cases identified (eg, participants with any elevated AST or ALT of >3 ULN and elevated Total bilirubin >2 ULN, 2 days apart), will be provided, displaying ALT, AST, Total bilirubin and ALP values.

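### The protocol does not say whether a Grade ≥3 ALT/AST rise attributed to liver metastases, and no worse than expected, is a mandatory AESI or not an adverse event at all

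*Protocol*

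**What the plan says.** **Rules that require reporting**
- Protocol 10.2, Table 9 note b: "All events of ≥ Grade 3 ALT/AST increase must be reported as an adverse event of special interest (AESI").
- Protocol 8.2.6.6 says the same of Grade ≥3 liver enzyme events, which it glosses as above 5 × ULN. Protocol 8.3.7 lists them as an AESI whether or not there are symptoms. None of the three makes an exception for cause.
- Protocol 8.3.1 requires AESIs to reach the sponsor within 24 hours.

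**Rules that exclude**
- Protocol 10.3.1, under events not meeting the AE definition, lists "Any clinically significant abnormal laboratory findings or other abnormal safety assessments that are associated with the underlying disease". The item carries a severity exception, so that it covers findings "that are associated with the underlying disease, unless judged by the Investigator to be more severe than expected for the participant's condition".
- Protocol 8.2.5 says disease-associated laboratory abnormalities do not count as clinically significant, with the same severity exception.

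**The links between them**
- Protocol 8.3.7: "An AESI is an AE (serious or nonserious) of scientific and medical concern specific to the Sponsor's product or program".
- Protocol 10.3.1, under events meeting the AE definition, includes results defined as an AESI. That item is one of the examples under a lead-in restricted to results "considered clinically significant in the medical and scientific judgment of the Investigator (ie, not related to progression of underlying disease").

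In SAP 3.6.2, liver AESIs are selected by an AESI tick box on the AE page of the eCRF.

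**The concern.** The liver AESI is meant to be an automatic trigger set by a laboratory grade. The general AE rules put an attribution step in front of it, taken by an investigator in a single-arm, open-label study. If a site decides that a finding is not an AE, it makes no entry on the AE page, so there is no box to tick and no 24-hour report.

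This matters most for participants with liver metastases. Exclusion criterion E 18 admits them with AST or ALT up to just under 5 × ULN, and the AESI threshold in 8.2.6.6 is above 5 × ULN. A small rise can cross the line in the group where tumour is the ready explanation. Hepatotoxicity is a named potential risk (2.3.1), and the protocol has no data monitoring committee (synopsis; 10.1.5), so expedited notification is one of the main routes by which the sponsor learns of such events promptly.

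**Working it through.** The plan states no expected AESI count, so there is no figure to reproduce. The check is a reading of the rules, case by case.

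**Step 1. Apply both sets of rules to a Grade ≥3 ALT/AST rise.**

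| Investigator's view of the rise | 8.2.6.6, 8.3.7, Table 9 note b | 8.2.5 and 10.3.1 exclusion | Conflict |
|---|---|---|---|
| Not due to underlying disease | AESI | Does not apply | No |
| Due to disease, more severe than expected | AESI | Lifted by the severity exception | No, in substance |
| Due to disease, no more severe than expected | AESI | Not clinically significant; not an AE | Yes |

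Only the third row is in conflict. Because 8.3.7 makes an AESI a kind of AE, an event in that row cannot satisfy both sets of rules.

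**Step 2. Ask whether the AESI item in 10.3.1 settles the third row.** It would if it stood alone. It is an example under a lead-in that requires clinical significance, explained as not related to progression of the underlying disease. Section 8.2.5 says that disease-associated findings are not clinically significant. On a literal reading the finding fails the lead-in before the AESI item is reached. No sentence gives an order of precedence.

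**Step 3. Trace the outputs.**
- Dependent on an AE-page entry: the AESI table, the related TEAE rows (both SAP 3.6.2) and the 24-hour report (Protocol 8.3.1).
- Not dependent on it: NCI grading of the worst on-treatment value from all measurements, the plot of peak ALT and AST against peak bilirubin, and the possible Hy's law listing (SAP 3.6.3.1).

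**Step 4. Scale.** With 38 planned participants, one participant counted or not moves AESI incidence by 1/38 = 2.6 percentage points. The number who could fall in the third row would be 38 × (proportion with liver metastases) × (proportion of those with a Grade ≥3 rise) × (proportion of those attributed to disease and as expected). The documents give none of these proportions, so the product cannot be formed.

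**Step 5. An illustration that AE-based and laboratory-based counts can differ.** Inputs are from Protocol 2.3.1, Table 1, for the earlier first-in-human study's pool at 100 mg/m² Q2W (186 patients).
- By laboratory value, AST Grade 3 in 9 and Grade 4 in 3: 9 + 3 = 12, taking the two grades as separate patients. The laboratory denominator implied by the percentages is 9/0.049 ≈ 184, so 12/184 = 6.5%.
- By Grade ≥3 TEAE, AST increased in 4: 4/186 = 2.2%. Adding transaminases increased (2) and hepatic cytolysis (2) with no overlap gives at most 8: 8/186 = 4.3%.
- Scaled to 38: 38 × 12/184 = 2.5 by laboratory grade, against 38 × 4/186 = 0.8 to 38 × 8/186 = 1.6 by AE report.

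If those terms are complete, at least 12 − 8 = 4 of the 12 had no matching Grade ≥3 TEAE. The documents do not say why, so this is not evidence that a disease exclusion caused the gap.

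**The case against.** The strongest reply is that the specific text points one way. Three liver-specific provisions require reporting without qualification. Section 10.3.1 defines an AE whether or not it is related to treatment and names AESI-defined results among laboratory AEs. Footnote d of the schedule of activities follows AESIs regardless of relationship with study treatment. Sections 8.2.5 and 10.3.1 are general text, and a site that reads note b has a clear instruction. Further, the hepatotoxicity signal does not rest on AE forms, because laboratory abnormalities are a secondary safety endpoint in their own right and are graded from all values.

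Much of this stands. It makes reporting the more likely reading, and it limits the exposure to the outputs named in Step 3. It does not supply a precedence rule: footnote d concerns follow-up of events already recorded, and the restriction on the AESI item in 10.3.1 remains.

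Some stronger readings are tempting but not supported:
- *That all participants with liver metastases are affected.* Only rises that are both attributed to tumour and considered no worse than expected are affected.
- *That the same data could give an AESI count of anywhere from none to two or three.* None would require every Grade ≥3 rise to be attributed to disease, none to be thought worse than expected, and every site to set note b aside. The 2.5 is borrowed from a study that Protocol 8.2.6.8 describes as covering several cancer types.
- *That those excluded have the least hepatic reserve.* The documents do not say so, and E 18 excludes total bilirubin above 1.0 × ULN (with an allowance for Gilbert's) even with liver metastases.
- *That the serious-event guide in 10.3.2, "ALT >3 × ULN + total bilirubin >2 × ULN or asymptomatic ALT increase >10 × ULN", contradicts the SAP listing of "participants with any elevated AST or ALT of >3 ULN and elevated Total bilirubin >2 ULN, 2 days apart".* Section 10.3.2 calls its list a guideline that is not exhaustive and leaves seriousness to medical judgement. AST rises of Grade ≥3 are already AESIs.

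**Conclusion.** The conflict is real but narrow. For a Grade ≥3 ALT/AST rise attributed to liver metastases and considered no more severe than expected, the protocol both requires an AESI report and says the finding is not an AE. The AESI count, the related TEAE rows and the 24-hour notification can therefore vary with the rule a site applies. Any error would lower the reported counts, since the exclusion can only remove events.

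The size is unknown, at 2.6 points of incidence per participant. The conclusion assumes that at least some sites would read 8.2.5 and 10.3.1 literally, which the documents neither confirm nor rule out. The primary endpoint, sample size, interim rule and laboratory-grade safety tables are unaffected. It is worth correcting because the liver AESI is a safety trigger in a trial without a control arm or monitoring committee, and the correction is cheap.

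**What to change.** 1. In Protocol 10.3.1, first item under events not meeting the AE definition, and in the parallel sentence of 8.2.5, add that the underlying-disease exclusion does not apply to AESIs (Section 8.3.7), which are recorded and reported whatever the attribution.
2. In 10.3.1, under events meeting the AE definition, move the AESI item outside the clause limited to findings not related to progression of the underlying disease.
3. Optionally, add to SAP 3.6.3.1 a listing of participants with laboratory Grade ≥3 ALT or AST and no ticked liver AESI. The SAP version history shows that enrolment began before the SAP was approved, so new protocol wording may not reach events already assessed; a listing would show them.

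The cost is protocol wording and, for item 3, one listing. The downside is a few more AESI forms and a slightly higher reported liver-event rate. No dosing or treatment rule changes.
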